5.3 Lifestyle Considerations

There are no restrictions regarding lifestyle.

5.4 Screen Failures

Screen failures are defined as participants who consent to participate in the clinical study but are not subsequently randomly assigned to study treatment/entered in the study. A minimal set of screen failure information is required to ensure transparent reporting of screen failure participants to meet the Consolidated Standards of Reporting Trials publishing requirements and to respond to queries from regulatory authorities. Minimal information includes demography, screen failure details, eligibility criteria, and any SAEs.

Individuals who do not meet the criteria for participation in this study (screen failures) may be rescreened. If a participant is being considered to be rescreened more than once, please contact the

Medical Monitor. Rescreened participants should not be assigned the same participant number as for the initial screening.

If a participant is considered for rescreening, the need for repeat testing should be discussed with the Medical Monitor. Upon approval by the Medical Monitor, if a participant is rescreened within 6 months a repeat chest X-ray is not required. If a participant is rescreened within 3 months, OCT does not need to be repeated if the participant does not have any visual symptoms, and PFTs do not need to be repeated if the participant does not have any respiratory symptoms.

6.0 STUDY TREATMENT

Study treatment is defined as any investigational treatment(s), marketed product(s), placebo, or medical device(s) intended to be administered to a participant according to the study protocol.

6.1 Study Treatment Description

The physical descriptions of study drug treatments are provided in [Table 7](#).

VTX002 tablets will be manufactured, quality control tested, and released in accordance with Good Manufacturing Practice.

Table 7 Study Treatment Description

Study Drug	VTX002	Placebo
Dosage Formulation	3 mg, 7 mg, 10 mg, and 20 mg Tablets	Matching placebo for 3 mg, 7 mg, 10 mg, and 20 mg Tablets
Dosage Level(s)	30 mg, 60 mg	Not applicable
Route of Administration	Oral	Oral
Dosing Instructions	Study drug should be taken by participants with approximately 240 mL (one cup) of water. The study drug can be taken with or without food. All doses on clinical days should be administered in the clinic.	Study drug should be taken by participants with approximately 240 mL (one cup) of water. The study drug can be taken with or without food. All doses on clinical days should be administered in the clinic.
Packaging and Labeling	Study treatment will be provided as orange tablets in weekly blister cards for Induction and LTE Periods (Weeks 0-52) of blinded treatment. Blister packs for dose titration for Weeks 0 and OLE Week 0 will have each day of the regimen labeled. Blister packs for assigned dose for Induction and LTE Periods (Weeks 1-52) will contain 7 rows of 4 tablets. Open-label bottles of 30 × 20 mg tablets or 100 × 20 mg tablets will be provided after conclusion of OLE Week 0 dose titration. Each blister/bottle will be labeled as required per country requirement.	Study treatment will be provided as orange tablets in weekly blister cards for Induction and LTE Periods (Weeks 0-52) of blinded treatment. Blister packs for assigned dose for Induction and LTE Periods (Weeks 1-52) will contain 7 rows of 4 tablets. Each blister will be labeled as required per country requirement.
Storage	15°C to 25°C 59°F to 77°F	15°C to 25°C 59°F to 77°F

6.2 Induction Treatment

6.2.1 Induction Treatment Week 0

Participants randomized to study drug will undergo a 7-day dose titration to receive their respective double-blinded drug doses (Days 1 to 7) in accordance to [Table 8](#) below. Although dose titration is not applicable for placebo and VTX002 30 mg after Day 6, the same number of tablets will be given to all participants to simulate dose titration and maintain blinding.

Table 8 Dose Titration in the Induction Treatment Period

Study treatment	Day 1 (Visit 2)	Day 2	Day 3	Day 4	Day 5	Day 6	Day 7	Day 8 and Onwards (Visit 3)
VTX002 30 mg	3 mg	7 mg	10 mg	14 mg	20 mg	30 mg	30 mg	30 mg
VTX002 60 mg	3 mg	7 mg	10 mg	14 mg	20 mg	30 mg	50 mg	60 mg
Placebo	Placebo	Placebo	Placebo	Placebo	Placebo	Placebo	Placebo	Placebo

Blister cards for Week 0 will contain 9 rows and up to 4 columns. Participants will take one tablet from each blister in the row for that day.

6.2.2 Induction and Long-Term Extension Treatment Weeks 1 to 52

Dosing configuration for Weeks 1-52 will contain 4 rows with 7 columns. Participants will take all tablets from each blister in the column for that day.

In the case where a participant attends a virtual visit (see [Section 8.2](#)) and requires additional study treatment to continue on the study, study treatment may be dispensed and delivered by an approved courier where permitted by local law and regulation. Alternatively, a future supply of study treatment may be dispensed to the participant at an onsite visit or an unscheduled dispensation visit to cover study treatment to be dispensed at the next planned virtual visit. Advanced planning and communication will be needed to dispense future supply of study treatment at an earlier onsite visit. Shipping guidelines and instruction will be provided separately.

6.3 Open-Label Extension Treatment

6.3.1 Open-Label Extension Dose Titration

Participants entering the OLE Treatment Period will undergo a 7-day dose titration (OLE Days 1 to 8) to receive VTX002 60 mg following the same titration schedule for the VTX002 60 mg as shown in [Table 8](#). Although dose titration would not be needed for participants who received VTX002 60 mg during the Induction Period/LTE Period, all participants entering the OLE Treatment Period will go through a full dose titration regimen to maintain the blind of the Induction Period/LTE treatment assignments.

6.3.2 Open-Label Extension Study Drug Supplies

Following titration to 60 mg, participants will be dispensed a sufficient number of bottles containing 30 or 100 tablets of VTX002 20 mg to provide drug until the next study visit. Participants will be instructed to take 3 tablets (60 mg) at the same time each day.

6.4 Additional Dosing Instructions

Study treatment should be taken at approximately the same time each day, preferably in the morning. Tablets should be taken with approximately 240 mL of water and can be taken with or without food. On study visit days, participants should wait and take their dose at the study site after all predose assessments and procedures have been completed, including blood draws for predose PK. The time of PK sample collection and last dosing prior to the PK sample should be documented. At Week 13 (Visit 8), study treatment administration should be performed in the clinic as part of the initial LTE visit.

6.4.1 Missed Dose Instructions

Participants should be instructed that if they forget to take a dose, they can take the dose within 8 hours of the normal dosing time; otherwise, they should take their next dose at the regular time on the following day. Participants who vomit a tablet should be instructed not to take another dose on the same day, but to take the next dose at the regular time on the following day. Participants will record their daily dose in a provided electronic diary (eDiary). Missed doses that occur at any time during a week prior to PK sampling should be recorded in the electronic Case Report Form (eCRF). Participants should be instructed to contact the Investigator if they miss more than 2 consecutive doses.

6.4.2 Dose Interruption

Decisions regarding dose interruptions will be made by the Investigator in consultation with the Medical Monitor based on the clinical evaluation of the participant.

If the Investigator deems it necessary to withhold study treatment, temporary withholding is permitted for up to 4 days without obtaining prior approval from the Medical Monitor. If study treatment interruption for ≥ 5 days is required due to a medical reason, the Investigator must contact the Medical Monitor.

The first-dose cardiac monitoring, as outlined in [Section 6.5.1](#), and dose titration as outlined in [Section 6.2.1](#), should be performed when study treatment dosing is interrupted as follows:

- Missed treatment ≥ 2 consecutive days within the first week of treatment or
- Missed treatment ≥ 5 consecutive days after the first week of treatment

6.5 Guidance for Cardiac Monitoring Following Treatment Initiation or Reinitiation

Prerandomization (ie, predose on Day 1) ECG should be performed and assessed prior to randomization.

Following treatment initiation or reinitiation, participants will remain in the clinic for at least 6 hours after study drug administration for safety assessments.

Prerandomization (ie, predose on Day 1) vital signs (ie, pulse, systolic and diastolic BP, temperature, and respiratory rate) will be used as baseline measurements. Pulse and BP will be measured using calibrated equipment (as appropriate) after the participant has been sitting for at least 5 minutes.

Atropine and epinephrine should be readily available at all study sites. Availability of emergency equipment should be within close proximity to study site. Personnel experienced in the use of advanced life support must be readily accessible during the first-dose monitoring (Week 0 [Day 1/Visit 2] and OLE Week 0 [OLE Day 1/OLE Visit 1]) and reinitiation of treatment, as well as in case of an emergency. A member of the Investigator team should be available to monitor the participant for the 6-hour monitoring period and report any abnormalities to the Investigator.

6.5.1 First-Dose Cardiac Monitoring

Participants will undergo in-clinic monitoring for at least 6 hours on Day 1 and OLE Day 1, with measurements taken prior to dose and at 1, 2, 4, and 6 hours (\pm 10 minutes) following study drug administration. Cardiac assessments should be performed as shown in [Table 9](#).

Participants experiencing a cardiovascular treatment-related symptomatic event (eg, chest pain, dizziness, palpitations, lightheadedness, shortness of breath, or syncope) associated with a clinically significant reduction of HR or associated with clinically relevant ECG changes at any time during the 6-hour monitoring period should be discontinued from treatment.

Participants will be released from the clinical site after dosing on Day 1 (Week 0/Visit 2) and OLE Day 1 (OLE Week 1/OLE Visit 1) when they fulfill the discharge criteria outlined in [Section 6.5.1.1](#), but no sooner than 6 hours postdose.

Table 9 Cardiac Assessments to Be Performed

Procedure	Clinic		Ambulatory
	Predose	1, 2, 4, and 6 hours postdose ^b	From 6 to 24 hours postdose
Vital signs ^a	X	X	
12-lead ECG	X	X	
Holter ECG monitoring ^c	X	X	X
Adverse events	X	X	
Assess discharge criteria		X ^d	

Abbreviations: BP = blood pressure; ECG = electrocardiogram

Note: The order of assessments should be rest for 5 minutes (sitting), vital signs (sitting), 12-lead ECG (supine), and then blood draws as applicable.

- Participants must be at rest for at least 5 minutes in sitting position. After the participant has been sitting for at least 5 minutes, pulse and BP will be measured.
- Measurements may be taken within ± 10 minutes of the scheduled time.
- Holter ECG monitoring will begin 1 hour predose and continue through 24 hours postdose. Participants who meet the discharge criteria ([Section 6.5.1.1](#)) at 6 hours postdose will be sent home for continued Holter ECG monitoring from 6 to 24 hours postdose.
- Discharge criteria assessed only at 6 hours postdose.

6.5.1.2 Extended Cardiac Monitoring

Participants who do not meet the discharge criteria at 6 hours postdose will require extended cardiac monitoring, as described below:

- Vital signs will be assessed hourly and 12-lead ECG may be performed, as clinically indicated, until the participant meets the discharge criteria ([Section 6.5.1.1](#)).
- Should a participant require pharmacologic intervention for symptomatic bradycardia, continuous overnight ECG monitoring in a medical facility should be instituted, and the first dose monitoring strategy should be repeated after the second dose of VTX002.
- Should postdose bradycardia (eg, HR < 50 bpm) or potentially related symptoms (eg, dizziness) occur, then initiate appropriate medical management, assess vital signs, begin continuous ECG monitoring, and continue observation until the symptoms have resolved.
- The Medical Monitor should be contacted if the participant does not meet the discharge criteria after ≥ 6 hours of extended cardiac monitoring.
- Any participant who requires extended monitoring on Day 1 (Week 0/Visit 2) or OLE Day 1 (OLE Week 0/OLE Visit 1) must return on the following day for the second dose and will be remonitored as on Day 1 (Week 0/Visit 2) or OLE Day 1 (OLE Week 0/OLE Visit 1), respectively. These participants will be discontinued from study treatment if they do not meet the discharge criteria at 6 hours after the second dose. Extended cardiac monitoring should be continued until the participant meets the discharge criteria ([Section 6.5.1.1](#)).
- Participants experiencing a symptomatic event (eg, chest pain, dizziness, palpitations, lightheadedness, shortness of breath, or syncope) during the 6-hour monitoring period that is not associated with either a reduction in HR or clinically relevant change in 12-lead ECG, and who continue to experience symptoms during the extended cardiac monitoring period, may be discharged provided the symptoms are not associated with a reduction in HR or clinically relevant changes in ECG during the extended cardiac monitoring period, and the Investigator deems it appropriate; however, these participants must return on Day 2/OLE Day 2 for the second dose and will be remonitored as on Day 1 (Week 0/Visit 2) or OLE Day 1 (OLE Week 0/OLE Visit 1). These participants should be discontinued from treatment if they do not meet the discharge criteria at 6 hours after the second dose on Day 2/OLE Day 2 or if they experienced the symptoms (eg, chest pain, dizziness, palpitations, lightheadedness, shortness of breath, or syncope) on Day 2/OLE Day 2, and extended cardiac monitoring should be continued until the participant meets the discharge criteria ([Section 6.5.1.1](#)).

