6.5.2 Study Treatment Discontinuation Related to Postdose Cardiac Monitoring

A complete list of reasons for study treatment discontinuation is provided in [Section 7.1](#). All treatment discontinuations should be discussed with the Medical Monitor.

Reasons for study treatment discontinuation specific to postdose cardiac monitoring include the following:

- Participants who have a cardiovascular treatment-related symptomatic event (eg, chest pain, dizziness, palpitations, lightheadedness, shortness of breath, or syncope) associated with a clinically significant reduction of HR or associated with clinically relevant 12-lead ECG changes at any time during the 6-hour monitoring period on Day 1/OLE Day 1 or Day 2/OLE Day 2 (as applicable).
- Participants who have not met the discharge criteria on Day 1 (Week 0/Visit 2) or OLE Day 1 (OLE Week 0/OLE Visit 1) after ≥ 6 hours of extended monitoring and on Day 2/OLE Day 2 by 6 hours postdose (see [Section 6.5.1.2](#)).

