 - If the ALC is confirmed to be below the 200 cells/ μ L limit, study treatment should be interrupted and should not be reinitiated if the ALC remains below this threshold. In this situation, the unblinded Medical Monitor will notify the Investigator and provide instructions on additional actions that the Investigator may need to take. When there is at least one measurement of ALC < 200 cells/ μ L, blinded values may be released to treating physicians and Investigators as deemed medically necessary to monitor infection and/or aid in diagnostic work-up as clinically indicated, and/or as a tool to assess the effectiveness of therapeutic interventions for an infection. Investigators will repeat CBC with differentials weekly until ALC > 500 cells/ μ L.
 - Reinitiation of study treatment can be considered only when ALC > 500 cells/ μ L.

A participant's study treatment must be discontinued permanently for any of the following reasons:

- Study participant is pregnant (see [Section 8.5.5](#))
- Decline in PFT values (FEV1 and/or FVC) below 50% of the predicted values
- Confirmed diagnosis of clinically significant macular edema, see [Section 8.4.6](#)
- Confirmed diagnosis of PML: Cases of PML have occurred in patients who have received S1P1 modulators. At the first sign or symptom suggestive of PML, withhold VTX002 and perform an appropriate diagnostic evaluation. The magnetic resonance imaging findings may be apparent before clinical signs or symptoms. Typical symptoms associated with PML are diverse, progress over days to weeks, and include progressive weakness on one side of the body or clumsiness of limbs, disturbance of vision, and changes in thinking, memory, and orientation leading to confusion and personality changes. The Investigator must notify the Medical Monitor of such symptoms.
- Cardiovascular events:
 - A participant experiencing a cardiovascular treatment-related symptomatic event (eg, chest pain, dizziness, palpitations, lightheadedness, shortness of breath, or syncope) associated with a clinically significant reduction of the HR or associated with clinically relevant 12-lead ECG changes at any time during the 6-hour monitoring period on Day 1 or Day 2 (as applicable) ([Section 8.4.3](#)). See also [Section 6.5](#) for cardiac monitoring during treatment initiation or reinitiation.

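### A participant treated for symptomatic bradycardia within 6 hours of the first dose, and still failing discharge criteria at hour 6, is told both to stop treatment and to take a second dose

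*Protocol*

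**What the plan says.** **The stop rule** appears in three places. Its trigger is a symptomatic cardiovascular event related to treatment, with a clinically significant fall in heart rate or a clinically relevant ECG change.

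- Protocol 6.5.1 says participants with such an event "at any time during the 6-hour monitoring period should be discontinued from treatment".
- Protocol 6.5.2 lists the event among the reasons for discontinuation, on Day 1 or Day 2 and on the corresponding days of the open-label extension (OLE).
- Protocol 7.1 puts it under the heading that a participant's "study treatment must be discontinued permanently for any of the following reasons".

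**The second-dose route** is in Protocol 6.5.1.2, which covers anyone who has not met the discharge criteria six hours after dosing. Three of its bullets matter here.

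- Symptomatic bradycardia needing a drug: the participant is kept overnight under ECG surveillance, after which "the first dose monitoring strategy should be repeated after the second dose of VTX002".
- Anyone needing extended monitoring on Day 1 or OLE Day 1: the participant "must return on the following day for the second dose and will be remonitored as on Day 1". Treatment is then stopped if the discharge criteria are not met six hours after that second dose.
- The last bullet also leads to a second dose, but only for a symptomatic event "during the 6-hour monitoring period that is not associated with either a reduction in HR or clinically relevant change in 12-lead ECG".

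**The concern.** The stop rule and the second-dose route have overlapping triggers and opposite actions. A site that applies 7.1 ends treatment for good. A site that applies 6.5.1.2 brings the participant back the next day for another dose, and on active drug that dose is higher than the one that caused the treated event.

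Decreased heart rate and atrioventricular conduction is the first risk listed in Protocol 2.3. In the Phase 1 single-dose cohorts the largest heart-rate fall came between 1 and 2 hours after dosing (Protocol 2.2.2.5), inside the window the stop rule covers. The study plans about 120 centers, so a first-dose safety instruction that can be read two ways may well be read both ways.

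**Working it through.** No figure in the plan needs reproducing. The check is whether one participant can satisfy both sets of conditions, and whether any text ranks them.

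**Test case.** On Day 1 or OLE Day 1, a participant has symptomatic bradycardia before hour 6. It is judged treatment-related, the heart-rate fall is clinically significant, a drug is needed, and the discharge criteria are not met at hour 6.

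| Provision | Trigger met? | Action |
|---|---|---|
| 6.5.1 | Yes: event is inside the 6-hour window | Discontinue (*should*) |
| 6.5.2, first bullet | Yes | Listed reason to discontinue |
| 7.1, permanent list | Yes, on Day 1 as written; OLE Day 1 is not named there but is covered by 6.5.1 and 6.5.2 | Discontinue permanently (*must*) |
| 6.5.1.2, opening line | Yes: discharge criteria failed at hour 6 | Extended monitoring |
| 6.5.1.2, drug-treated bradycardia | Yes: no time limit on onset is stated | Repeat monitoring after the second dose |
| 6.5.1.2, any participant in extended monitoring | Yes | Return next day for the second dose (*must*) |
| 6.5.1.2, last bullet | No: heart rate is reduced | Not applicable |

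The first three rows and the two second-dose rows cannot all be followed.

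**Is there a tie-breaker?**

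- Strength of wording does not settle it, because *must* appears on both sides.
- Specificity points the wrong way. The drug-treated bullet is the only text that names symptomatic bradycardia needing a drug.
- 6.5.2 refers to 7.1 for the full list of reasons, and 7.1 refers back to 6.5. Neither ranks the rules.
- 6.5.2 asks for discontinuations to be discussed with the Medical Monitor, but a site following 6.5.1.2 has no discontinuation to discuss. Within 6.5.1.2, contact with the Medical Monitor is called for only after at least 6 hours of extended monitoring without meeting the criteria.
- The SAP does not address the point.

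**The exclusion exists, but in one bullet only.** The last bullet of 6.5.1.2 keeps participants with a heart-rate or ECG effect off its second-dose route. The other two second-dose bullets carry no such limit.

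**Dose step.** From Table 8 (Protocol 6.2.1), both active arms receive 3 mg on Day 1 and 7 mg on Day 2: 7 / 3 = 2.33-fold.

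**Who takes that step.** Two active arms of about 63 give 2 × 63 = 126 of 189 randomized participants. The 63 on placebo have no active second dose in Induction. Every OLE entrant, former placebo participants included, follows the same schedule under Protocol 6.3.1. These are the people exposed to the step, not a count of events.

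**A related mismatch.** The symptomatic-event bullet in 7.1 names only Day 1 and Day 2. For the same event, 6.5.2 also names OLE Day 1 and OLE Day 2, and the next bullet of 7.1 names the OLE days too. Since 6.5.1 and 6.5.2 already cover the OLE, this is editorial.

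**The case against.** The best reply is that the structure shows which rule was meant to win. Sections 6.5.2 and 7.1 each give two cardiac stop routes: an in-window symptomatic event with a heart-rate or ECG effect, and failure of the discharge criteria on Day 1 and again on Day 2. Only the second refers to 6.5.1.2, so the second dose belongs to that route, and a permanently discontinued participant has no second dose. The narrow scope of the last bullet of 6.5.1.2 fits this reading. It is probably what the authors intended. It is still inference, and it does not override an instruction that says any participant in extended monitoring must return for the second dose.

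It can also be said that the drug-treated bullet concerns interventions after hour 6, outside the stop rule, and fixes the timing of monitoring rather than ordering a dose. That is a fair reading and makes it the weaker of the two bullets. The bullet on any participant in extended monitoring creates the conflict without it.

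There are other safeguards. Section 8.0 sends immediate safety concerns to the Sponsor to decide whether treatment continues. Section 6.4.2 lets the Investigator withhold drug for up to 4 days without prior approval. Section 7.1 allows discontinuation by Investigator decision. These make a mistaken second dose less likely. They permit or prompt a stop; none says that the stop rule prevails.

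Finally, the case is likely to be uncommon. In the Phase 1 single-dose cohorts heart rate was back to baseline by Hour 3, and the largest fall came at 40 mg against 3 mg here, although those were healthy volunteers. Participants who enter the OLE directly from 60 mg are not meeting the drug for the first time. Both points limit the expected number of cases and leave the contradiction in place.

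**Conclusion.** The concern holds. For a treatment-related symptomatic bradycardia that begins before hour 6, is treated with a drug and still fails the discharge criteria at hour 6, the protocol requires both permanent discontinuation and a second dose the next day, with no order of precedence. Followed literally, 6.5.1.2 re-doses a participant whom 7.1 says must be stopped, at 7 mg after 3 mg if on active drug.

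This rests on two readings. First, *clinically significant* heart-rate reduction is not defined, and symptomatic bradycardia needing a drug is taken to meet it. Second, the event is judged treatment-related. No error is claimed for events that begin after hour 6, where the second-dose route works without conflict, or for the separate bullet on heart rate below 50 bpm or dizziness. No event count is claimed, because the documents give no rate. It should be fixed, because it is a first-dose safety instruction and the correction is simple.

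**What to change.** In 6.5.1.2, add the following to both the drug-treated bradycardia bullet and the bullet on any participant who requires extended monitoring: *unless the participant meets a discontinuation criterion in 6.5.2 or 7.1, in which case no second dose is given.* The second-dose route then serves only participants who have not already been stopped, such as those whose bradycardia begins after hour 6.

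In 7.1, add OLE Day 1 and OLE Day 2 to the symptomatic-event bullet so that it matches 6.5.2.

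The cost is one clause in two bullets, a longer day list in a third, and a memo to sites. No procedure, data collection or sample size changes.
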